We expect that these co-primary hypotheses may relate to one another in at least two ways, although we do not have specific predictions as to how this interrelation may manifest (see *Figure 2*). First, the SSIs' effects on parent treatment-seeking and youth internalizing symptoms may relate *inversely* to one another, due to *differential* intervention effects on each outcomes. That is, the SSIs might positively influence youth problems *or* parent treatment-seeking, depending on which effects are more rapidly apparent to the family. For instance, if effects on youth internalizing symptoms emerge more rapidly and overtly than effects on parent treatment-seeking, parents may in turn be less inclined to seek additional care. Likewise, if effects on youth symptoms fail to emerge within a short period of time, parents may be *more* inclined to seek additional care after completing the parent-directed SSI. Thus, is it possible that effects may emerge for *either* parent treatment-seeking *or* youth symptoms, but not both. Conversely, it is possible that the SSIs may positively affect parent treatment-seeking and youth

internalizing symptoms *simultaneously*. If parents perceive initial symptom reductions in their child following the SSI, these initial improvements—indicating the potential for further gains—may *further* motivate them to seek additional care. We perceive both pattern of results as equally plausible in the present trial; either would help clarify the potential role(s) of these SSIs within pediatric primary care.

In addition to our co-primary hypotheses, we will also test two secondary hypotheses to further contextualize the intervention's effects and acceptability. We predict that (3) IPR+SSI will reduce parental stress and psychological distress across 3-month follow-up, versus IPR alone, and (4) families will rate this service delivery model as acceptable.

Method

Study Design. This study will be a two-arm randomized-controlled trial with 1 active intervention condition and 1 active control condition (1:1 allocation ratio). Procedures were pre-registered on ClinicalTrials.gov on 7/24/2019 (NCT04030897; anticipated date of first enrollment: 12/15/2019). The University Institutional Review Board (#IRB2019-00241) approved all study procedures on 7/8/2019. Project funding is provided by the Klingenstein Third Generation Foundation.

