Youths and parents will complete all study procedures remotely via personal internet-equipped devices. After discussing procedures with a research team member via telephone, eligible families will receive a study link from which parents and youths may provide consent and assent and complete their respective study portions. In separate Qualtrics-based surveys, parents and youths will complete baseline questionnaires, the GM-SSIs (or 'waitlist' notification; IPR will be provided to all families at initial PC appointments), and post-intervention questionnaires within a single online survey lasting approximately one hour per family member. Parent-youth pairs will both be assigned to the same condition (GM-SSI or 'waitlist') via survey-embedded random-number generators; randomization will not be stratified. Subsequently, three-month follow-up questionnaires will be administered via Qualtrics-based surveys. Follow-up surveys will assess parents' treatment-seeking behaviors, youth symptoms, parental stress and psychopathology, and related variables (detailed below). Families who do not complete follow-up surveys

within 3 days of contact will receive ≤ 3 reminder messages. After completion of the 3-month follow-up, families who did not initially receive GM-SSIs will be granted intervention access.

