Participants and Recruitment. We will recruit two-hundred youths ages 11-16 and one parent per youth from nine community-based branches of the University Hospital's Pediatric Primary Care service. Per the University Medical Center's policies, providers at all sites administer the youth-report Pediatric Symptom Checklist (PSC)¹³ to patients 11 and older. Providers review patients' PSC scores during their appointments; all youths reporting symptom elevations receive an "Information, Psychoeducation, and Referral" folder, including contact information for local mental health providers and psychoeducational materials. In this study, youths with an elevated PSC-Internalizing Score (5/10 or higher, per 0-2 ratings of five items: *Feel sad or unhappy, feel hopeless, down on yourself, seem to be having less fun, worries a lot*) may be eligible for participation, per existing PSC-Internalizing cut-offs.¹⁴ Because the PSC is already implemented and scored across participating clinics, and because PSC scores are used to direct distribution of "Information, Psychoeducation, and Referral" resource folders to patients, using the PSC as an eligibility screen creates no added clinical burden for providers. Within 3 weeks of the youth's PC appointment, a research team member will contact potentially eligible families by phone to introduce the study and invite them to participate. Additional inclusion criteria, assessed during this call, include English-language proficiency and comfort completing computer-based activities. Receipt of mental health services upon enrollment will be monitored but will not preclude participation.

The parent- and youth-directed interventions last approximately 15-30 minutes. Thus, there is no plan to discontinue interventions due to worsening symptoms, but participants will be informed that they may stop participating in the study at any time without penalty.

Sample size justification. First, using G*Power 3.1, we calculated samples needed to achieve 80% power to detect a small (per Cohen's recommendations: $d=.2$ or $OR=1.49$), medium ($d=.5$ or $OR=3.45$), and large effects ($d=.8$ or $OR=9.00$) effect on primary outcomes (parent treatment-seeking behaviors, per logistic regression, and youth depressive symptoms, per linear regression) at $\alpha=.05$ for a two-arm RCT, including two covariates (baseline youth depression symptom severity; intervention

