condition). *N*s were 392, 55, and 25, respectively, for a regression predicting, and 615, 89, and 50, respectively, for a logistic regression predicting parent treatment-seeking behaviors at 3-month follow-up. However, it is necessary in this study to consider our multisite recruitment structure (9 sites total). GM-SSIs have previously produced small-to-medium improvements in youth depressive symptoms and parent treatment expectancies; we thus used procedures outlined by Feaster, Mukulich-Gilbertson, and Brincks¹⁵ to obtain more precise power estimates for a mixed-effects model predicting medium up ($d = 0.5$) changes in youth depressive symptom severity from baseline to 3-month follow-up, assuming low variability in treatment across sites (0.05). A target *N* of 246 (approximately 26-28 youths per site, although we cannot accurately project exact site-specific recruitment totals in advance) would ensure 92% power to detect an average intervention effect of $d = 0.5$ and 80% power to detect a minimum average effect size of $d = 0.42$. As such, a target *N* of 246 was selected for this study. Notably, participants will be randomized at the study level—not at the site level—ensuring an even number of families assigned to both study conditions overall.

Intervention Descriptions

Youth-Directed Growth Mindset (GM) SSI.¹⁰ The web-based, youth-directed GM-SSI is delivered via Qualtrics and is approximately 30 minutes long. All activities are self-administered and delivered in a web-based format, including illustrations, graphics, and audio-recordings. Content is designed to maximize relevance for youths experiencing depressive symptoms (e.g., sadness, hopelessness) and includes five components: 1. A brief lesson on neuroplasticity, describing how behaviors are controlled by thoughts and feelings in the brain, and thus have potential for change; 2. Stories from older youths describing beliefs that their traits (e.g., sadness, anxiety) are malleable; 3. Further stories by older youths, describing times when they applied this knowledge to cope with emotional setbacks; 4. Scientific studies suggesting that personality can positively change over time; and 5. An exercise in which participants write notes to younger peers, using newly-gleaned knowledge to generate advice on coping with an emotional setback. Here, youths are presented with a hypothetical peer rejection scenario and respond to the following prompt: “How do you think you would feel if this

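### The plan says randomization ensures equal arms, but the allocation mechanism it describes contains nothing that would produce them

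*Combined protocol and SAP*

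**What the plan says.** Study Design in the combined protocol and SAP sets a 1:1 allocation ratio and makes the family the unit: "Parent-youth pairs will both be assigned to the same condition". Assignment is made "via survey-embedded random-number generators; randomization will not be stratified".

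The sample size justification fixes the target ("As such, a target *N* of 246 was selected for this study") over nine sites, with "approximately 26-28 youths per site, although we cannot accurately project exact site-specific recruitment totals in advance". It closes by saying that randomization takes place at study level rather than site level, "ensuring an even number of families assigned to both study conditions overall".

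The Analytic Plan puts recruitment site into the treatment-seeking and youth-symptom models as a random effect and carries the same structure over to the parent stress and distress models. No section describes blocks, quotas, an urn, minimization or a pre-generated list.

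**The concern.** The level at which families are randomized does not produce equal arm counts. Only a restriction on the sequence does. With independent draws, 1:1 is an expectation, and the realized split will nearly always differ from 123:123. The plan thus asserts a property that its described mechanism does not supply.

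The main stake is an accurate statement. A reader who later sets the final arm counts beside this sentence would probably find a mismatch and could wrongly suspect an allocation failure. A secondary stake is balance within the nine sites. The plan does not promise it, but the same change to the allocation could provide it. The document is a Stage 1 report that gives its first-enrollment date as anticipated, so both can still be settled.

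**Working it through.** **Inputs.** N = 246, nine sites, treatment variability across sites 0.05, alpha 0.05, and power of 92% at d = 0.5 and 80% at d = 0.42 (all from Sample size justification); 1:1 ratio and unstratified generator (Study Design). Assumptions: two-sided test, outcome SD of 1, 0.05 read as a variance on the d scale, normal approximation, independent draws.

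**1. The plan's own power.** With J = 9 sites of m = 246/9 = 27.3 families and equal arms in each:

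- SE² = (0.05 + 4/27.3)/9 = 0.1963/9 = 0.0218, so SE = 0.1477
- d = 0.5: Φ(0.5/0.1477 − 1.96) = 92.3%
- d = 0.42: Φ(0.42/0.1477 − 1.96) = 81.2%

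Both agree with the stated figures to within two points.

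**2. Overall balance under independent draws.** The count in one arm is Binomial(246, 0.5).

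| Quantity | Result |
|---|---|
| P(exactly 123:123) | 5.1% |
| SD of the arm difference, √246 | 15.7 families |
| 95% range of the split | 108:138 to 138:108 |
| P(difference ≥ 10) | 57% |
| P(difference ≥ 20) | 23% |
| P(difference ≥ 30) | 6.4% |

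Participants and Recruitment gives a target of 200 instead of 246. At N = 200 the chance of exact equality is 5.6%, so that discrepancy does not affect this point.

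**3. Balance within sites.** For a site of 27, Binomial(27, 0.5) gives a 95% range of 8 to 19 in one arm and P(18:9 or worse) = 12.2%. With nine such sites, the chance that at least one splits this badly is 1 − (1 − 0.122)⁹ = 69%. Blocking at study level alone changes this little: the hypergeometric probability is 10.1% per site, or about 62% for any of nine.

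**4. Cost of an overall imbalance.** A 108:138 split has an effective N of 4 × 108 × 138/246 = 242.3, which is 98.5% of 246. Power at d = 0.5 becomes 92.0% instead of 92.3%.

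**5. Cost of imbalance within sites.** Step 1 was repeated with 1/n₁ + 1/n₂ for each site in place of 4/m, averaged over simulated simple randomizations (40,000 for near-equal sites, 20,000 for uneven sites). The uneven pattern is an assumed example: 70, 50, 40, 30, 20, 14, 10, 7 and 5 families.

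| Sites | Effect | Simple | Site-stratified blocks |
|---|---|---|---|
| Six of 27, three of 28 | 0.5 | 91.6% | 92.3% |
| Six of 27, three of 28 | 0.42 | 80.0% | 81.1% |
| Uneven example | 0.5 | 88.3% | 89.3% |

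For near-equal sites, the 2.5th percentile of power under simple randomization is 90.7% and 78.7%. The lower level in the last row comes from the uneven site sizes. The part due to allocation is again about one point.

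**6. What blocks would deliver.** Take blocks of 4 and 6 within site. At position j of a block of size B, the variance of the arm difference is j(B − j)/(B − 1). Averaged over stopping positions this is 0.83 for B = 4 and 1.17 for B = 6, or (4 × 0.83 + 6 × 1.17)/10 = 1.03 when weighted by length. Over nine sites the SD of the overall difference is √(9 × 1.03) ≈ 3 families, against 15.7. No site can be off by more than 3.

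**The case against.** The strongest reply is that unstratified does not mean unrestricted. The survey tool may force even counts, and the sentence on equal numbers may be describing exactly that. This stands: that the generator makes independent draws is an inference. It turns the overall-balance point into one of missing detail, because the restriction would then have to be stated. Imbalance within sites would remain.

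It can also be said that the plan claims balance only overall and openly declines stratification, which is a disclosed and valid choice. This stands too. Stratifying by site is an improvement on offer, not the correction of a contradiction.

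A reader might infer three stronger points, none of which the documents support:

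- *That the power figures depend on equal arms within sites.* The plan states no such assumption and says site totals cannot be projected. Mean power under simple randomization with near-equal sites is 91.6% and 80.0%, in line with the stated 92% and 80%.
- *That lopsided sites carry little information.* An 18:9 site keeps 4 × 18 × 9/27² = 88.9% of a balanced site's information. With the 0.05 treatment variance included, the site's variance rises from 0.05 + 4/27 = 0.198 to 0.05 + 1/18 + 1/9 = 0.217, so about 91% is kept.
- *That site differences contaminate the arm comparison.* Assignment is random, so there is no bias in expectation, and the models already carry a random effect for site.

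**Conclusion.** The point holds as an unsupported guarantee, not as a threat to power or validity. Nothing described in the plan ensures equal arms. Under independent draws, exact equality has about a 1 in 20 chance, and a difference of 20 or more families has about a 1 in 4 chance. The price is about 0.3 power points for a 108:138 split and about one point for chance imbalance within sites.

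The overall-balance figures rest on the generator being unrestricted, and the site figures on nine sites of about 27. The power reproduction depends on how 0.05 is read. As a variance with a normal approximation it gives 92.3% and 81.2%; as a variance with t on 8 df, 84.1% and 70.3%; as an SD with t on 8 df, 92.4% and 81.5%. That ambiguity concerns the level of power and is separate from the question of allocation.

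**What to change.** Preferred: generate permuted blocks of varying size by computer (for example 4 and 6), load them into the survey platform with the family as the unit, and stratify by recruitment site, since site is already in the models. Amend the Study Design sentence that rules out stratification, and describe the arms as near-equal overall and within sites.

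The costs are modest. Site, and one assignment shared by the separate parent and youth surveys, must be available to the allocation logic. A few blocks will be left incomplete, so equality will be close and not exact. Predictability is a minor concern, because allocation is remote and the research team is blinded to condition.

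If the existing generator already forces even counts, say how. If simple randomization is kept, change one sentence: claim an expected 1:1 ratio in place of a guarantee, and state the expected imbalance (SD of the difference about 16 families; 95% range about 108:138 to 138:108 at N = 246).

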Trial conduct. Data will be monitored on an ongoing basis (daily) for quality assurance purposes and to ensure protocol compliance. Further, we will follow University IRB policies for expedited adverse event (AE) reporting. The PI will review data for potential AEs in real-time throughout the trial; AEs occurring during the study will be reported to the IRB within 48 hours. Any protocol alterations that become necessary will be approved by the IRB before implementation.

Data confidentiality and sharing statement. Data will be collected via Qualtrics and stored on password-protected electronic servers meeting University security standards. After the funding period concludes, de-identified participant-level data will be posted publicly via Open Science Framework (OSF). Intervention materials are available from the first author upon request.

Measures (see **Table 1** for SPIRIT information).

Mental Health Treatment-Seeking Checklist (Co-Primary Outcome). At baseline and 3-month follow-up, parents will indicate their engagement ('yes'/'no') in four treatment-seeking behaviors for their child: researched local mental healthcare providers/agencies; contacted mental healthcare provider or agency about treatment; contacted child's school regarding mental health supports; and scheduled an appointment *or* placed child on waiting-list with a mental healthcare provider/agency (number of treatment-seeking behaviors ranges from 0-4). At baseline, parents will report whether they engaged in these behaviors since the child's PC appointment, and at follow-up, since their last survey. Parent treatment-seeking will be a primary outcome.

Children's Depression Inventory-2 (CDI-2; Co-Primary Outcome). Parents and youths will complete the CDI-2 scale at baseline (pre-intervention) and 3-month follow-up. The CDI-2 is a reliable, valid measure of youth depression severity, normed for youth age and sex and yielding raw and T scores, along with an index of functional impairment. The CDI-2 is highly sensitive to clinical change across treatment and is used routinely in clinical trials for treating youth depression.^{3,7,10} Change in self-reported youth depressive symptoms will be a primary outcome; parent-reported youth depression symptoms is a secondary outcome.

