Mental Health Treatment Access. Parents will indicate (yes/no) whether their child has received (a) new and/or (b) continuing school-based, outpatient, or other mental health-related services since the child's recent PC appointment (at baseline) and since the baseline assessment (at follow-up).

Perceived Stress Scale. The PSS is a validated measure of one's appraisal of daily life as stressful, unpredictable, and uncontrollable.^{27,28} At baseline and follow-up, parents will rate 10 items from 0-4, with higher scores indicating greater perceived stress (range: 0-40).

Implicit Theories of Emotion Scale. The ITE Scale^{29,30} will serve as a manipulation check for the parent-directed GM-SSI. At baseline and post-intervention (IPR+SSI group only), parents will report the degree to which they view emotions as malleable (versus immutable) on a 1-6 scale across four items. Higher mean scores (range: 1-6) indicate stronger fixed emotion mindset, and lower scores, stronger growth emotion mindset.

Implicit Theories of Personality Questionnaire. The ITPQ³¹ will be used as a manipulation check for the youth-directed GM-SSI. At baseline and post-intervention (IPR+SSI group only), youths will rate agreement with three statements linked to malleability of personality. Higher mean scores indicate stronger fixed personality mindsets, and lower scores, stronger growth personality mindsets (range: 1-6).

Intervention Feedback Scale. Immediately post-intervention, the Intervention Feedback Scale³² will ask youth and parents receiving GM-SSIs to indicate how much they enjoyed, understood, felt helped by, would recommend, and agreed with the program's message. They will also be prompted to provide written feedback regarding their impressions of the program.

Adverse Childhood Experiences (ACEs). The ACEs questionnaire is a well-validated measure of exposure to violence, childhood emotional, physical, or sexual abuse, and household dysfunction during childhood.^{33,34} Parents will complete the ACEs questionnaire at baseline in reference to their child and to themselves.¹

¹ We do not plan to use the ACEs questionnaire in primary study analyses. Rather, we are including this questionnaire to allow for future tests of whether trauma exposure influences GM-SSI intervention

Demographics. Parents will report family and background information (e.g. youth age, sex, mental health treatment history).

Analytic Plan

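### No listed measure asks about adverse events and nothing is scheduled between the baseline sitting and month 3, so interim events surface only if volunteered; the 48-hour reporting window has no stated start

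*Combined protocol and SAP*

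**What the plan says.** Trial conduct gives the whole of the AE plan. It states that "we will follow University IRB policies for expedited adverse event (AE) reporting", then that "The PI will review data for potential AEs in real-time throughout the trial" and that "AEs occurring during the study will be reported to the IRB within 48 hours". Separately, "Data will be monitored on an ongoing basis (daily) for quality assurance purposes and to ensure protocol compliance". The IRB policies are not reproduced. The section does not define an AE, does not say how AEs are elicited, and does not say when the 48 hours begin.

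Study Design sets the timing of data. Baseline measures, the intervention or waitlist notice, and the immediate post-intervention measures are completed together: "post-intervention questionnaires within a single online survey lasting approximately one hour per family member". The next step is "Subsequently, three-month follow-up questionnaires will be administered via Qualtrics-based surveys". Families who do not respond "within 3 days of contact will receive ≤ 3 reminder messages". Table 1 shows no contact between these two points.

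The Measures section and Table 1 list no adverse-event item. The nearest question about events is Mental Health Treatment Access, a parent yes/no on new or "continuing school-based, outpatient, or other mental health-related services since the child's recent PC appointment" (at follow-up, since the baseline assessment). The Analytic Plan names no harms analysis.

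**The concern.** The only means of finding AEs that the plan describes is reading study data, and those data are neither designed to reveal AEs nor collected during the three months when most would occur. The participants are youths aged 11 to 16 selected for elevated internalizing symptoms and followed remotely, so acute events such as self-harm or an emergency visit are foreseeable. If the plan is followed exactly and no family volunteers an event, such an event may leave no trace. A low AE count at the end would then say little about how many events occurred.

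The reporting window has a related problem. Without a stated start, the team could be compliant or in breach on the same facts, depending on how the sentence is read.

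**Working it through.** The plan states no figure on this point, so there is none to reproduce. The check sets the schedule against the AE statements, then works out what the 48-hour window means under each reading.

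**1. When data arrive for one family.** Study Design and Table 1 give one sitting of about an hour per family member, then one survey at three months. Taking three months as 90 to 92 days (assumption), the interval without scheduled data is 90 × 24 = 2,160 to 92 × 24 = 2,208 hours. Frequent checking of the database does not shorten that interval for an individual family.

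**2. What the month-3 data can show.** 
- The youth CDI-2, PSC and BHS-4, and the parent BSI-18, PSS and BHS-4, are collected at baseline and month 3 in both arms. They can show worsening present at month 3. They cannot show an episode that occurred and resolved in between.
- Mental Health Treatment Access is also collected in both arms. It asks for no date or reason. Because Hypothesis 1 predicts more treatment-seeking under IPR+SSI, a yes cannot by itself be read as harm.
- No item yields an AE as such, so there is nothing to tabulate under that name by arm.

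**3. What is collected in one arm only.** The post-intervention BHS-4, the youth and parent writing exercises, and the written feedback exist only in IPR+SSI. All fall within the baseline sitting. Immediate reactions therefore have no counterpart in the control arm. After that sitting, each arm has the same single scheduled wave.

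**4. The 48-hour window.** 
- *Clock from occurrence.* Assume event times are uniform over the interval and the event is first seen at the month-3 survey. Share reportable in time = 2 days / interval length: 2/90 = 2.22%, 2/91 = 2.20%, 2/92 = 2.17%. Mean lag from event to survey = half the interval: 45, 45.5 and 46 days. Late response after reminders lengthens the lag by an amount the plan does not fix.
- *Clock from awareness.* Incoming data are looked at daily. Even counting from submission of the survey, a daily look uses at most about 24 hours, leaving 48 − 24 = 24 hours to report. The window can be met.

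**5. Families with no month-3 survey.** They have no scheduled source of AE information after the baseline sitting. The plan gives no expected non-response rate, so no size is attached to this.

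**The case against.** The strongest reply is that the plan does not promise continuous surveillance of each participant. It promises that data are reviewed as they arrive. With rolling recruitment projected from January 2020 and follow-up to June 2021, data do arrive throughout the trial. The phrase about AEs occurring during the study may only define which events are reportable, and the preceding sentence defers to IRB policies that may say when the clock starts. A reporting route may also be given in the consent materials, which are not available here. All of this stands. A reader might infer that both the real-time and the 48-hour promises fail, or that about 98% of interim events would be reported late; the documents do not support either. The second figure needs a clock from occurrence, which the text does not state, and no spontaneous reports, which the text does not exclude.

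A second reply is that harm can be compared by arm through the symptom scales and service use at month 3. This also stands, so it would be wrong to infer that harms cannot be compared at all. What is missing is any pre-specified comparison, and any source for acute events that have resolved.

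A third tempting inference is that IPR+SSI gets three looks and control two, so that every by-arm count is distorted. The additional look lies inside the same one-hour sitting. For later events scheduled ascertainment is equal, and the imbalance is confined to immediate reactions.

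None of these replies supplies a way of detecting an interim event. As described in the protocol, expedited reporting governs an event once it is known.

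**Conclusion.** The point holds as a gap in ascertainment and an undefined clock. Detection is described only as review of study data. Those data contain no AE item and leave about 90 to 92 days per family without a scheduled observation, so an acute interim event reaches the team only if someone volunteers it. AEs as such cannot be tabulated by arm. Deterioration and new service use can be, but the plan does not commit to it.

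The 48-hour window is workable from awareness. From occurrence it would be out of reach for all but about 2.2% of interim events, given uniform event times, first detection at month 3 and no spontaneous reports. That figure shows why the start must be stated; it does not predict late reporting. The conclusion does not depend on the content of the IRB policies or consent materials, except on whether a between-survey reporting route and a clock start already exist there. The efficacy analyses and sample size are unaffected.

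**What to change.** 1. Add the same short, fixed AE block to the month-3 survey in both arms, at least by parent report, asking about specified events since the last survey with approximate dates. Any youth self-harm item should be subject to the IRB's existing response procedures. Define an AE in the protocol to match.
2. State that the 48 hours run from the team's awareness, and describe real-time review as review of data as they arrive at the two contact points.
3. Pre-specify a by-arm table of AEs and of deterioration on the CDI-2, PSC and BHS-4, drawn from sources common to both arms. List events found only in IPR+SSI material separately. For the CDI-2 use youth report unless Table 1 is corrected: it does not mark the parent form at follow-up, although the Measures text does.
4. If the consent materials do not already do so, name one reporting route open to all families between surveys.

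The cost is a slightly longer follow-up survey, an IRB amendment, attention to the response procedure if youths are asked about self-harm, and a monitoring statement that claims less than the present one. The interventions, sample size and primary analyses do not change.
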